## List of Abbreviations

Abbreviation	Definition
5-HT 1A	5-hydroxytryptamine 1A
5-HT 2A	5-hydroxytryptamine 2A
ALT	alanine aminotransferase
AST	aspartate aminotransferase
AUC_%Extrap	percentage of AUC due to extrapolation from $t_{last}$ to infinity $[(AUC_{\infty} - AUC_t)/AUC_{\infty} \times 100]$
AUC ∞	area under the concentration-time curve from time zero to infinity
AUC τ	area under the concentration-time curve during a dosing interval ( $\tau$ ) at steady-state
AUC t	area under the concentration-time curve calculated to the last observable concentration at time t
BMI	body mass index
CGI-I	Clinical Global Impression - Global Improvement
CGI-S	Clinical Global Impression - Severity of Illness
CL/F	apparent clearance of drug from plasma after extravascular administration
C max	maximum (peak) plasma concentration of the drug
CPK	creatine phosphokinase
C-SSRS	Columbia-Suicide Severity Rating Scale
CYP2D6	cytochrome P450 2D6
CYP3A4	cytochrome P450 3A4
DIEPSS	Drug Induced Extra-Pyramidal Symptoms Scale
DNA	deoxyribonucleic acid
DSM-5®	Diagnostic and Statistical Manual of Mental Disorders Fifth Edition
EDC	electronic data capture
EDTA	ethylenediaminetetraacetic acid
EM	extensive metabolizer
FBR	Future Biospecimen Research
FDA	(United States) Food and Drug Administration
FT 4	free thyroxine
GCP	Good Clinical Practice
IB	investigator brochure
ICH	The International Council for Harmonisation of Technical Requirements for Pharmaceuticals for Human Use
ICMJE	International Committee of Medical Journal Editors
IM	intermediate metabolizer
IRE	immediately reportable event
IWRS	interactive web response system
LSMD	least square mean difference
$\lambda_z$	apparent terminal-phase disposition rate constant (first-order)
OD	orally disintegrating
OROS	osmotic-controlled release oral delivery system

Abbreviation	Definition
PANSS	Positive and Negative Syndrome Scale
PM	poor metabolizer
PQC	product quality complaint
QTc	corrected QT interval
QTcI	individually corrected QT interval
QTcF	QT interval corrected for heart rate using Fridericia's formula
QW	quaque (once) weekly
$t_{1/2,z}$	terminal-phase elimination half life
TEAE	treatment-emergent adverse event
$t_{last}$	time of last measurable (positive) concentration
$t_{max}$	time to maximum plasma concentration
TSH	thyroid-stimulating hormone

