#### **4.5      Definition of Completed Subjects**

The treatment period is defined as the time period during which subjects are evaluated for primary and/or secondary objectives of the trial. Subjects who are evaluated at the last scheduled visit during the treatment period will be defined as trial completers. For the purposes of this trial, subjects who complete Day 14 blood sampling for plasma drug concentration measurement in Period 2 will be defined as trial completers.

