## 5 Statistical Analysis Sets

## 5.1 Food Effect Analysis Set

The food effect analysis set includes all subjects for whom  $C_{max}$ ,  $AUC_{\infty}$  or  $AUC_t$  could be calculated throughout Period 1 and Period 2.

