## 5.3 Handling of Missing Data

No imputation procedures will be applied for missing data.

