### 2) Statistical Analysis Methods

The natural log-transformed  $C_{max}$ ,  $AUC_{\infty}$ , and  $AUC_t$  of brexpiprazole in plasma will be analyzed using a linear mixed-effects model with group (fasting-state-administration-first group or fed-state-administration-first group), meal condition (fasting or fed), and period (Period 1, Period 2) as fixed effects, and within-group subjects as a random effect, and the differences in means of natural log-transformed values between meal conditions (fed-state administration – fasting-state administration) and their two-sided 90% confidence intervals will be calculated. The differences in the mean natural log-transformed values (fed-state administration – fasting-state administration) and their two-sided 90% confidence intervals will be inverse-transformed to calculate the ratio of geometric mean values (fed-state administration/fasting-state administration) and two-sided 90% confidence interval. The Kenward-Roger method will be used for approximation of the degrees of freedom.

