## 10.3 Technical Details for Pharmacokinetic Statistical Analysis

### 1) Exclusion of Data

The following data will be rejected and excluded from pharmacokinetic analyses:

- [REDACTED]
- Plasma drug concentrations after use of prohibited concomitant medications or foods that may affect the PK of brexpiprazole, and pharmacokinetic parameters calculated using rejected concentrations
- Plasma drug concentrations after failure to receive the IMP according to the conditions specified in the protocol (Section 5.3.1 and Section 6.1.2), and pharmacokinetic parameters calculated using rejected concentrations
- Plasma drug concentrations in samples collected outside the protocol-specified acceptable window (Table 1.3-2) of blood sampling time points. These data will be excluded from the calculation of descriptive statistics of concentrations at the time points, but will be used for the calculation of pharmacokinetic parameters.
- Plasma drug concentrations and pharmacokinetic parameters in a period for compounds for which the predose plasma drug concentrations exceed 5% of  $C_{max}$  during that period
- Plasma drug concentrations or pharmacokinetic parameters judged to be inappropriate by the clinical pharmacologist for other reasons than the above. In this case, the reason for judging them to be inappropriate will be recorded.

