## **3) Handling of Plasma Drug Concentrations at Withdrawal and Unscheduled Visits**

- If blood sampling for measuring plasma drug concentrations at withdrawal or unscheduled visits is performed outside the acceptable window of scheduled visits, the data will be handled as withdrawal or unscheduled visit data. In accordance with [Section 10.2 2\) a\)](#), descriptive statistics will not be calculated for plasma drug concentrations at withdrawal or unscheduled visits.
- If blood sampling for measuring plasma drug concentrations at withdrawal or unscheduled visits is performed within the acceptable window of scheduled visits and no data are available at the scheduled visits, the data obtained at the withdrawal or unscheduled visits will be handled as scheduled visit data.

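### Does letting AUCt stop at each period's own last concentration, with no written rule for short profiles, undermine the primary fed/fasting comparison?

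*Protocol*

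**What the plan says.** The Protocol's List of Abbreviations defines AUCt as the "area under the concentration-time curve calculated to the last observable concentration at time t" and tlast as the "time of last measurable (positive) concentration". Neither fixes a common end time.

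SAP 10.1 models log Cmax, AUC∞ and AUCt, and for the fed-minus-fasting differences "their two-sided 90% confidence intervals will be calculated". Under SAP 5.1 (and Protocol 9.2.1) a subject belongs to the food effect analysis set if Cmax, AUC∞ or AUCt "could be calculated throughout Period 1 and Period 2". SAP 5.3 adds: "No imputation procedures will be applied for missing data".

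Being a completer is not a condition for entering that set, and it depends on Period 2 only. Protocol 4.5: "subjects who complete Day 14 blood sampling for plasma drug concentration measurement in Period 2 will be defined as trial completers".

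SAP 10.3 3) deals with samples taken at withdrawal. It settles which visit they count towards and says that "descriptive statistics will not be calculated for plasma drug concentrations at withdrawal or unscheduled visits". It does not mention AUCt.

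SAP 10.3 1) lists data to be rejected. One bullet is blacked out. The last readable one covers "Plasma drug concentrations or pharmacokinetic parameters judged to be inappropriate by the clinical pharmacologist for other reasons than the above" and requires the reason to be recorded.

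**The concern.** Take a subject with sampling to 312 h in Period 1 and only to 120 h or 168 h in Period 2. The two AUCt values cover different stretches of time, so their ratio is pulled away from the food effect by the missing tail. Nothing readable stops that ratio from entering the primary model.

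If short profiles fall on fed and fasting periods alike, the geometric mean ratio (GMR) stays centred, but the within-subject variance rises and the 90% CI widens. If they fall mainly on one meal condition, the GMR moves towards a lower value for that condition. Restricting to completers would not help, because a short Period 1 profile is compatible with completer status. A subject who leaves in Period 1 has no Period 2 data and is not in the set. The exposure is therefore Period 2 withdrawals, and late samples missed or rejected in either period.

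**Working it through.** **Inputs.** From the documents: 36 completers (Protocol 4.1), 1:1 allocation (taken as 18 per sequence), limits 0.80 to 1.25 and no food effect (Synopsis, Sample size), last sample at 312 h (Table 1.3-1). The CV, power, half-life and absorption rate are not readable. Assumed: within-subject CV 20–30%, half-life 60–150 h, ka 0.02–0.1/h.

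**1. The plan's own figure.** Without the CV and power, 36 can only be bracketed. With σ = √ln(1+CV²), SE = σ√(2/N) and 34 df, the chance that the 90% CI lies within the limits at N = 36 is 99.8% at CV 20%, 96.6% at 25%, 87.0% at 30% and 72.2% at 35%.

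**2. How much AUC a short profile loses.** For one compartment with first-order absorption, AUC(0–T) ∝ (1−e^(−ke·T))/ke − (1−e^(−ka·T))/ka. As a share of AUC(0–312), over 24 combinations (half-life 60, 75, 90, 110, 130, 150 h; ka 0.02, 0.03, 0.05, 0.1/h):

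| Profile ends at | Share of AUC(0–312) |
|---|---|
| 120 h | 0.40–0.74 |
| 168 h | 0.60–0.86, median about 0.71 |
| 240 h | 0.83–0.96 |

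At 168 h only 1 of the 24 combinations is as low as 0.60.

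**3. Keep one short subject, or drop the subject?** At CV 25%, σ² = ln(1.0625) = 0.0606, so the variance of the period difference is 2σ² = 0.1213. One subject with log shift δ = ln(share) in a sequence of 18 adds δ²(17/18)/34 to the pooled variance.

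- Share 0.75: δ² = 0.0828, added 0.0023, half-width × √(1 + 0.0023/0.1213) = 1.009.
- Share 0.55: δ² = 0.357, added 0.0099, half-width × √(1 + 0.0099/0.1213) = 1.040.

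Simulated mean log half-widths agree: 0.0974 with all spans equal, then 0.0975, 0.0984, 0.1015 and 0.1066 with one profile at share 0.90, 0.75, 0.55 and 0.40. Dropping the subject gives 0.0989, a factor of 1.015.

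Break-even: δ² = (1.0154² − 1) × 0.1213 × 34 × 18/17 ≈ 0.135, so the share is e^(−0.368) ≈ 0.69. Above that, keeping the short profile costs less than dropping it.

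For that one subject the GMR shifts by δ/36 on the log scale. At share 0.55 this is −0.598/36 = −0.017, a GMR of about 0.98.

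**4. Three short Period 2 profiles on top of 36 completers**, random by sequence, CV 25% (simulated):

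| Case | Log CI width | Chance CI within 0.80–1.25 |
|---|---|---|
| 36 completers only | 0.195 | 0.967 |
| plus three at 0.60 | 0.201 | 0.955 |
| plus three at 0.75 | 0.192 | 0.973 |
| plus three at 0.90 | 0.187 | 0.977 |

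At 0.71, the typical 168 h share, the width is 0.193 to 0.194, level with 36 completers alone. At share 0.60 the chance moves from 0.997 to 0.995 at CV 20% and from 0.870 to 0.866 at CV 30%. If all three fall on fed periods (0.5³ = 0.125), the GMR is 0.965 and the chance 0.933 at CV 25%.

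**5. What a common cut-off would do.** Suppose food slows ka from 0.05 to 0.03/h with equal extent of absorption. The fed/fasting ratio is then 0.97–0.99 at 312 h, 0.93–0.95 at 168 h and 0.89–0.90 at 120 h. Cutting both profiles early removes the span mismatch but reads slower absorption as lower exposure.

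**The case for a change.** The strongest argument for acting is that discretion is not a rule. In an open-label trial the clinical pharmacologist could keep or reject a primary ratio after seeing it, and two SAP sentences would end that. The plan can also shorten a profile itself: concentrations after prohibited drugs or foods are rejected, and the text does not say whether an AUCt recalculated from earlier samples remains valid. Bad cases exist too. Two profiles at share 0.40 in the same sequence lower the chance of meeting the limits to 83.5% at CV 25%, with a GMR of 0.951.

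What stands is that no readable criterion is set in advance. The rest weakens on inspection. A share of 0.40 needs an end at 120 h at the slowest corner of the assumed range, or an earlier end, and no passage suggests several such subjects. Each period has one dose, so stopping treatment after the Period 2 dose does not end sampling. Protocol 7.3.4 keeps subjects in follow-up where possible unless they withdraw completely, and Protocol 1.3.2.6 calls for a withdrawal examination. Table 1.3-1 shows outpatient attendance only for the late samples, so a missed visit mostly means an end at 168 h or 240 h, where keeping the subject costs little or nothing. The blacked-out bullet cannot be counted as missing.

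Nor is the remedy clear. A common cut, a minimum tlast and exclusion each have a cost, and the common cut errs most at early stops, the only place where a rule would matter.

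**Conclusion.** The observation about the text is correct: AUCt spans can differ between a subject's two periods, and the readable plan leaves short profiles to case-by-case judgement. It does not call for a change. This is an unwritten rule for a rare case, which a pharmacokineticist can handle sensibly under SAP 10.3 with the reason on record. Unequal spans would not be hidden, since AUC∞ is also primary and tlast and AUC_%Extrap are summarised by meal condition.

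At an assumed CV of 25%, a short profile does net harm only below about 70% of AUC(0–312). Three added profiles at 60% lower the chance of meeting the limits by about one percentage point if random by sequence, and by about three if all are fed. Profiles ending at 240 h are negligible. A complete-profile sensitivity analysis would be a harmless extra check, but it would not correct a wrong result. These sizes rest on assumed CV, half-life and absorption ranges and a one-compartment shape, because the sponsor's values are blacked out. Many profiles ending by about 120 h, concentrated in one meal condition, would alter the conclusion.

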## 1 Protocol Summary

### 1.1 Synopsis

**Name of Sponsor:** Otsuka Pharmaceutical Co., Ltd.

**Name of Investigational Medicinal Product:** Brexpiprazole (OPC-34712)

**Protocol No.:** 331-102-00151

**Protocol Title:**

A multicenter, randomized, open-label, 2-arm, 2-period crossover trial to investigate the effects of food on the pharmacokinetics of a single dose of brexpiprazole once-weekly (QW) formulation in patients with schizophrenia

**Protocol Lay Person Short Title:**

A food effects trial of the pharmacokinetics of brexpiprazole once-weekly (QW) formulation in patients with schizophrenia

**Clinical Phase/Trial Type:**

Phase 1/clinical pharmacology trial

**Planned Treatment/Indication:**

Schizophrenia

**Trial Rationale:**

Brexpiprazole conventional tablets, a once-daily oral formulation, has demonstrated efficacy and safety in the treatment of schizophrenia in clinical trials in subjects with schizophrenia conducted in Japan, the US, and Europe and is approved in Japan and overseas as a treatment for schizophrenia. In the treatment of schizophrenia, maintenance of drug compliance is thought to be instrumental in alleviating symptoms and achieving favorable outcomes; however, in comparison with other chronic diseases, schizophrenia is generally associated with poor drug adherence due mainly to lack of consciousness of disease and cognitive impairment. Long-acting drugs have been introduced into clinical practice as a measure to improve patient adherence to medication, but currently the only commercially available long-acting antipsychotics are all injectable formulations, thus reflecting an unmet medical need for more easy-to-use long-acting antipsychotics. Otsuka is now developing a once-weekly (QW) formulation, utilizing the same less invasive route of administration as conventional brexpiprazole, namely the oral route, but with a different formulation to enable reduced dosing frequency.

Otsuka has conducted clinical pharmacology trials to investigate the pharmacokinetics (PK), tolerability, and safety of the brexpiprazole QW formulation administered as single and multiple oral doses in Japanese patients with schizophrenia and confirmed the tolerability and safety of the drug. Based on the PK results, Otsuka has made dose selection and is currently conducting a phase 3 confirmatory trial to investigate the efficacy and safety of the brexpiprazole QW formulation in patients with acute schizophrenia.

According to “Clinical Pharmacokinetic Studies of Pharmaceuticals” (Evaluation and Licensing Division, Pharmaceutical and Medical Safety Bureau [PMSB/ELD] Notification No. 796, dated 01 Jun 2001), “Drug Interaction Guidelines for Drug Development and Proper Informatics,” (Pharmaceutical Evaluation Division, Pharmaceutical Safety and Environmental Health Bureau [PSEHB/PED] Notification No. 0723-6, dated 23 Jul 2018), and “Guidelines for Design and Evaluation of Sustained-Release (Oral) Preparations” (Notification. No. 5 of the First Evaluation and Registration Division, PAB dated 11 Mar 1988), there is a requirement to investigate the effects of food on the final drug product, and therefore it was decided to evaluate food effects in this trial. Additionally, the design of this trial was made with reference to various guidance and guidelines, and tests and endpoints are items that are commonly performed.

Based on the above, the conduct of the planned trial based on this protocol is judged to be scientifically and ethically appropriate.

### **Objectives and Endpoints:**

To investigate the effect of food on the PK of a single dose of brexpiprazole QW formulation at 48 mg in patients with schizophrenia and to confirm safety under those conditions.

Objectives	Endpoints
Primary objective: To investigate the effect of food on PK of a single dose of brexpiprazole QW formulation at 48 mg in patients with schizophrenia	Primary pharmacokinetic endpoint: Geometric mean ratio and two-sided 90% confidence interval of $C_{max}$ , $AUC_{\infty}$ , and $AUC_t$ of brexpiprazole in plasma after administration in a fed state versus administration in a fasting state Secondary pharmacokinetic endpoints: 
 
Plasma concentrations of brexpiprazole and metabolite [REDACTED]
 
Pharmacokinetic parameters of brexpiprazole and metabolite [REDACTED] in plasma
 

Objectives	Endpoints

Secondary objective: To confirm safety of the brexpiprazole QW formulation in patients with schizophrenia
	
Safety endpoints:
 
 
• Adverse events (AEs)
 
• Clinical laboratory tests
 
• Vital signs (body temperature, blood pressure, and pulse rate)
 
• Physical examination findings
 
• Body weight
 
• Body mass index (BMI)
 
• 12-Lead electrocardiography (ECG)
 
• Drug Induced Extrapyramidal Symptoms Scale (DIEPSS)
 
• Columbia-Suicide Severity Rating Scale (C-SSRS)
 
 
Other endpoints:
 
 
• Clinical Global Impression-Severity of Illness (CGI-S)
 
• Clinical Global Impression - Global Improvement (CGI-I)
 
• Bowel-movement investigation
 

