**Table 3-1 Trial Objectives and Endpoints**

Objectives	Endpoints

Primary objective:
 
To investigate the effect of food on PK of a single dose of brexpiprazole QW formulation at 48 mg in patients with schizophrenia
	
Primary pharmacokinetic endpoint:
 
Geometric mean ratio and two-sided 90% confidence interval of <math>C_{max}</math>, <math>AUC_{\infty}</math>, and <math>AUC_t</math> of brexpiprazole in plasma after administration in a fed state versus administration in a fasting state
 
Secondary pharmacokinetic endpoints:
 
 
Plasma concentrations of brexpiprazole and metabolite [REDACTED]
 
Pharmacokinetic parameters of brexpiprazole and metabolite [REDACTED] in plasma
 

Table 3-1 Trial Objectives and Endpoints	
Objectives	Endpoints
Secondary objective: To confirm safety of the brexpiprazole QW formulation in patients with schizophrenia	
Safety endpoints:
 
 
• AEs
 
• Clinical laboratory tests
 
• Vital signs (body temperature, blood pressure, and pulse rate)
 
• Physical examination findings
 
• Body weight
 
• BMI
 
• 12-Lead ECG
 
• DIEPSS
 
• C-SSRS
 
 
Other endpoints:
 
 
• CGI-S
 
• CGI-I
 
• Bowel-movement investigation
 

BMI = body mass index; CGI-I = Clinical Global Impression - Global Improvement; CGI-S = Clinical Global Impression-Severity of Illness; C-SSRS = Columbia-Suicide Severity Rating Scale; DIEPSS = Drug Induced Extrapyramidal Symptoms Scale.

[Section 9.4](#) describes the statistical analysis of the endpoints.

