## 10.2 Statistical Analyses of Secondary Pharmacokinetic Endpoints

### 1) Endpoints

- a) Plasma concentrations of brexpiprazole and metabolite [REDACTED]
- b)  $C_{max}$ ,  $AUC_{\infty}$ ,  $AUC_t$ ,  $t_{max}$ ,  $t_{1/2,z}$ ,  $CL/F$ ,a  $CL/F/BW$ ,a  $t_{last}$ ,  $AUC\%_{Extrap}$ , and  $\lambda_z$  of brexpiprazole and metabolite [REDACTED] in plasma
- c) Ratios of the AUC ( $AUC_{\infty}$  and  $AUC_t$ ) of metabolite [REDACTED] to that of brexpiprazole

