### 2) Statistical Analysis Methods

Descriptive statistics will be calculated as described below. However, if more than half of the subjects in an analysis set are excluded from summarization due to missing values, not calculable, or rejected data, descriptive statistics to be calculated for that parameter will include only the number of subjects in the analysis set and the number of subjects tabulated.

- a) Plasma drug concentration
  - For 1) a), descriptive statistics will be calculated at each blood sampling time point excluding the withdrawal and unscheduled time points by meal condition and compound.
  - The descriptive statistics to be calculated will include the number of subjects in the analysis set, the number of subjects tabulated, arithmetic mean, standard deviation, coefficient of variation, minimum, median, and maximum.
- b) Plasma PK parameters (except for  $\lambda_z$ )
  - For 1) b), descriptive statistics will be calculated by meal condition and compound.
  - For 1) c), descriptive statistics will be calculated by meal condition.
  - The descriptive statistics to be calculated will include the number of subjects in the analysis set, the number of subjects tabulated, arithmetic mean, standard deviation, coefficient of variation, geometric mean, minimum, median, and maximum. However, descriptive statistics to be calculated for  $t_{max}$  and  $t_{last}$  will be the number of subjects in the analysis set, the number of subjects tabulated, minimum, median, and maximum.

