CT-10.3	Shift Tables of Clinical Laboratory Test Results - Qualitative Urinalysis (Safety Analysis Set)
CT-10.4.1	Incidence of Potentially Clinically Significant Abnormalities in Laboratory Tests (Safety Analysis Set)
CT-10.4.2	Listing of Potentially Clinically Significant Abnormalities in Laboratory Tests (Safety Analysis Set)
CT-10.5.1	Incidence of Hy's Law Cases (Safety Analysis Set)
CT-10.5.2	Listing of Hy's Law Cases (Safety Analysis Set)
CT-11.1	Descriptive Statistics for Vital Signs (Safety Analysis Set)
CT-11.2.1	Incidence of Potentially Clinically Significant Abnormalities in Vital Signs (Safety Analysis Set)

[figure not shown]
CT-11.2.2	Listing of Potentially Clinically Significant Abnormalities in Vital Signs (Safety Analysis Set)
CT-12.1	Descriptive Statistics for 12-Lead ECG Parameters (Safety Analysis Set)
CT-12.2	Shift Table of 12-Lead ECG Findings (Safety Analysis Set)
CT-12.3	Incidence of Categorical Changes in 12-Lead ECG - QTcF (Safety Analysis Set)
CT-12.4.1	Incidence of Potentially Clinically Significant Abnormalities in ECG Evaluations (Safety Analysis Set)
CT-12.4.2	Listing of Potentially Clinically Significant Abnormalities in ECG Evaluations (Safety Analysis Set)
CT-13.1	Descriptive Statistics for Body Weight and BMI (Safety Analysis Set)
CT-13.2.1	Incidence of Potentially Clinically Significant Abnormalities in Body Weight (Safety Analysis Set)
CT-13.2.2	Listing of Potentially Clinically Significant Abnormalities in Body Weight (Safety Analysis Set)
CT-14	Descriptive Statistics for DIEPSS (Safety Analysis Set)
CT-15	Summary of Suicidality in C-SSRS (Safety Analysis Set)
CT-16.1	Listing of Subjects whose CGI-S has Worsened (Safety Analysis Set)
CT-16.2	Listing of Subjects whose CGI-I has Worsened (Safety Analysis Set)
PKT-1.1	Individual and Summarized Brexpiprazole Plasma Concentrations Following Single Oral Administration of Brexpiprazole QW Formulation (Food Effect Analysis Set)
PKT-1.2	[REDACTED]
PKT-2.1	Individual and Summarized Brexpiprazole Plasma Pharmacokinetic Parameters Following Single Oral Administration of Brexpiprazole QW Formulation (Food Effect Analysis Set)
PKT-2.2	[REDACTED]
PKT-3	Summary of Geometric Mean Ratio with Two-sided 90%CI for Brexpiprazole Pharmacokinetic Parameters (Food Effect Analysis Set)
PKF-1.1	Mean Brexpiprazole Plasma Concentrations Following Single Oral Administration of Brexpiprazole QW Formulation (Food Effect Analysis Set)
PKF-1.2	[REDACTED]

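### The metabolite's PK parameters serve the food-effect objective, but the readable plan gives them no fed/fasting ratio with a within-subject 90% confidence interval

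*Protocol*

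**What the plan says.** Protocol Table 3-1 states the primary objective as "To investigate the effect of food on PK of a single dose of brexpiprazole QW formulation at 48 mg in patients with schizophrenia". The wording is not limited to the parent compound. In the same row, the table and the synopsis list metabolite concentrations and "Pharmacokinetic parameters of brexpiprazole and metabolite" as secondary PK endpoints. SAP Table 2-1 repeats this. Protocol 8.2.1 has parent and metabolite measured in the same plasma samples, and the schedule takes those samples at the same nominal times in both periods.

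The comparative analysis is narrower. In SAP 10.1 the log-transformed Cmax, AUCinf and AUCt "of brexpiprazole in plasma will be analyzed using a linear mixed-effects model with group", meal condition and period as fixed effects and subject within group as random. Protocol 9.4.3.2.1 has the same model. The matching output, PKT-3, is titled "Summary of Geometric Mean Ratio with Two-sided 90%CI for Brexpiprazole Pharmacokinetic Parameters (Food Effect Analysis Set)".

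For the secondary PK endpoints, SAP 10.2 2) b) says "For 1) b), descriptive statistics will be calculated by meal condition and compound". The item that opens "Ratios of the AUC" concerns metabolite relative to parent, not fed relative to fasting, and for it the plan says "For 1) c), descriptive statistics will be calculated by meal condition". The statistics named include a geometric mean per meal condition, but no ratio between conditions and no interval. Protocol 9.4.3.2.2 agrees.

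Among the data that SAP 10.3 rejects are "Plasma drug concentrations and pharmacokinetic parameters in a period for compounds for which the predose plasma drug concentrations exceed 5% of" Cmax in that period. This rule works compound by compound.

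**The concern.** A two-period crossover lets each subject serve as their own control, so a food effect can be estimated free of between-subject variation. For the metabolite the paired data will exist, but no planned output uses the pairing. A reader who wants to know how food changes metabolite exposure gets two geometric means, each with a spread that mixes between-subject and within-subject variation. The standard deviations by condition do not show how fed and fasting values correlate within subjects, so no within-subject interval can be recovered from the summaries.

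A second issue could arise from the rejection rule. A subject may keep both periods for brexpiprazole and lose one for the metabolite, and nothing is imputed (SAP 5.3). The fed and fasting metabolite means would then rest on different subjects.

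**Working it through.** There is no figure in the plan to reproduce on this point. The sample size rationale is redacted, and no variability is readable for either compound. All CVs below are assumptions.

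**Inputs from the documents.** 36 completers (protocol 4.1, SAP 3.1); 1:1 allocation, taken as 18 per sequence; two-sided 90% intervals.

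**1. Point estimate from the planned summaries.** With complete pairs and equal sequence sizes, the difference of the two log geometric means equals the average of the two sequence-specific mean fed-minus-fasting differences. Each meal condition then has half its values from each period, so an additive period effect cancels. This is the crossover estimate. With complete, balanced pairs, only the interval is missing.

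**2. Interval the crossover could give.** On the log scale, half-width = t(0.95, 34) × s_w × √(2/36), where s_w² = ln(1 + CV_w²), t = 1.691 and √(2/36) = 0.2357.

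| Within-subject CV | s_w | Half-width | Ratio multiplied or divided by |
|---|---|---|---|
| 20% | 0.198 | 0.0789 | 1.08 |
| 25% | 0.246 | 0.0981 | 1.10 |
| 30% | 0.294 | 0.1170 | 1.12 |
| 35% | 0.340 | 0.1355 | 1.15 |

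**3. What a reader could get from the summaries.** Treating the two conditions as independent samples, half-width = t(0.95, 70) × s_t × √(2/36), where t = 1.667 and s_t² = ln(1 + CV_t²).

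- Total CV 40%: s_t = 0.385, half-width 0.1514, factor 1.16.
- Total CV 60%: s_t = 0.555, half-width 0.2179, factor 1.24.

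On the log scale this is between 0.1514/0.1355 = 1.1 and 0.2179/0.0789 = 2.8 times as wide as the paired interval. The plan does not propose such an interval. The comparison only shows what is lost if the summaries are all a reader has.

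**4. Effect of losing metabolite periods.** Simulation: 20,000 trials, 18 per sequence, true ratio 1, no period effect, total CV 50%, within-subject CV 25%. Selected subjects lose their Period 2 metabolite value, and the ratio of the remaining marginal geometric means is averaged on the log scale.

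| Subjects losing Period 2 | Ratio of marginal means |
|---|---|
| None | 1.00 |
| 2 highest-exposure, fasting-first sequence only | 0.963 |
| 4 highest-exposure, fasting-first sequence only | 0.938 |
| 2 highest in one sequence, 1 in the other | 0.98 |
| 2 or 4 highest in each sequence | 1.00 |
| 2 or 4 at random, one sequence only | 1.00 |

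In every row the within-subject contrast on complete pairs averages 1.00. If the highest subjects are instead picked on their observed Period 1 value, loss of 2 or 4 from one sequence gives marginal ratios of about 0.97 and 0.95, and within-subject contrasts of about 1.01 and 1.02.

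**The case against.** The strongest reply is that nothing promised is missing. The geometric mean ratio and its interval are defined as the primary endpoint for brexpiprazole only. The secondary endpoints are named simply as concentrations and parameters, and both documents say openly and consistently that these will be summarised descriptively. Parent tmax, half-life and clearance are handled the same way. This stands: it is a gap between objective and analysis, not a contradiction or an error.

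A reader might infer that the metabolite food effect will be biased. The documents do not support that. Bias needs loss that is both unequal between sequences and related to exposure. Carry-over would act in Period 2 of both sequences, and the rule compares predose with Cmax, so high exposure alone does not trigger it. Nothing readable shows how often it would reject the metabolite and spare the parent. SAP 10.2 also reports the number of subjects tabulated, so unequal counts would be visible.

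A reader might also infer that no metabolite comparison will ever be possible. That too goes further than the text. PKT-2.2 is redacted. If it is the metabolite counterpart of PKT-2.1, it lists individual values, and a ratio could be computed afterwards, though not as a prespecified analysis. Protocol 9.4.3.6 and SAP 13 are redacted as well; their headings (exploratory and other endpoints) and the table list give no sign of a second ratio table.

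Finally, the metabolite's identity is redacted, so its importance cannot be judged from the documents. That limits the weight of the point but does not remove it, because the sponsor placed the metabolite under the food-effect objective.

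**Conclusion.** The point holds as an inexpensive improvement. In the readable plan, an analyte listed under the food-effect objective has no planned fed/fasting ratio and no within-subject interval. The loss is mainly of precision: the available interval factor is about 1.08 to 1.15 for an assumed within-subject CV of 20% to 35% with 36 complete pairs, and none is planned. The point estimate is at risk only if metabolite periods are lost unequally between sequences. The 0.96 to 0.94 figures illustrate that one-sided case under assumed CVs and should be read beside the 1.00 for equal loss. The primary brexpiprazole analysis is not affected.

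**What to change.** In SAP 10.2 2) b), add that the SAP 10.1 mixed model, with the same fixed and random effects and Kenward-Roger degrees of freedom, will also be fitted to natural-log metabolite Cmax, AUCinf and AUCt. The log metabolite/parent ratios of AUCinf and AUCt may be included as an option. Report fed/fasting geometric mean ratios with two-sided 90% confidence intervals beside PKT-3, labelled supportive and with no equivalence claim. Keep the descriptive tables as they are. If the sponsor considers that the metabolite needs no fed/fasting estimate, a sentence giving the reason would also close the gap.

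The cost is about two sentences in the SAP and one further block in an existing table. It uses the same model code and data already collected, needs no extra subjects or samples, and leaves the primary analysis unchanged.
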